8.1 Screening and baseline visit (bv)

Staging examinations have to be conducted at first to review the requirements for participation in the study. On the basis of endoscopy of the stomach and bowel with histologically proven disease, CT scans of thorax and abdomen for identification of stage, in case of fulfillment of inclusion and lacking exclusion criteria, informed consent of the patient has to be obtained before the start of treatment. The treating oncologist informs the patient in a comprehensible way about his diagnosis, state of the art examinations and therapy as well as the objectives of the study (s. chapter 13.2).

The intended effect and possible side effects of treatment have to be pointed out. It has to be guaranteed that the patient understands his/her free choice to participate in the study, that informed consent may be withdrawn at any time and that the non-participation in the study results in no disadvantages for the patient. In case of consent, the patient has to be aware that data from his/her medical record are drawn for documentation, surveillance of the study and further analysis. The extent and purpose of analyzed data has to be made clear.

Patients should be encouraged to report all medical conditions during and after the RT in possible causality to the treatment to the treating physician. Information on follow-up visits and examinations after treatment have to be given on first contact, the results of which should be transmitted to the study management (see chapter 1.1 study contact).

Permission to anonymous data transfer between participating study sites or further attending physicians and the study management, and data analysis by the study center, is explicitly granted by the patient in the context of his written informed consent in study participation. It also includes the permission for the study center to contact the patient directly or his/her general practitioner in case of missing data to fulfill the study objectives.

Informed consent has to be given in writing and also will be signed by the treating physician. The patient informed consent form, after signature by the patient and the treating physician (plus witness, if present), will be archived.

Copies of the informed consent and the patient information on the study are given to the patient.

After having signed the informed consent form, patients will undergo anamnesis interview, clinical examination and blood analysis to assess baseline parameters.

A patient must provide written consent before undergoing any protocol-required assessments.

The baseline visit should include the assessment of quality of life with QLQ-C30 and STO-22.

The baseline visit includes blood draw!

The **baseline visit** and the routine (staging) procedures prior to treatment include:

- Anamnesis
 - Symptoms and date of onset
 - B-symptoms
 - Diagnosis and therapy of Helicobacter pylori
 - Medication (especially acid secretion inhibitors and antibiotics) and time of prescription
- Clinical examination
 - Quality of life assesment of QLQ-C30 and STO-22
 - Performance status (ECOG-status)
 - Body weight, blood pressure
 - Palpation of peripheral lymph nodes liver, spleen and abdomen
- Blood analysis
 - Complete blood count
 - LDH, GOT, GPT, alcalic phosphatase, γ -GT, bilirubin, creatinine, protein electrophoresis, total protein, albumin, immunoelectrophoresis
 - Serum protein, ferritin, vitamin B12, folic acid (in case of anemia)
 - **Blood draw (at baseline visit):**
 - **–Research program (analyses at the University of Muenster!): Two 7.5 - 9 ml serum monovettes.**
Centrifugation, freezing and storage see 3.1.3 and Appendix 16.7 (SOP BLOOD SAMPLES for RESEARCH PROGRAM)
Transmission of frozen blood samples to Radiobiology lab, Muenster at the cost of Dept. of Radiation Oncology, University Hospital Muenster).
- Imaging
 - CT-scan thorax and abdomen
 - abdominal and cervical ultrasound
 - planning CT for radiation
- Endoscopy
 - esophagogastroduodenoscopy (with biopsy)
 - endosonography upper GI-tract (EUS)
 - video capsule endoscopy
 - (ileo)colonoscopy (to evaluate additional disease within GI-tract)
- Quality of life
 - QoL assesment with QLQ-C30 and STO-22

8.1.1 Compulsory examinations in case of suspected involvement

- ENT examination
- Liver biopsy
- Bone scan
- Ileocolonoscopy with biopsies
- Video Capsule Endoscopy
- CT head/neck
- bronchoscopy
- liquor puncture
- MRI
- Bone marrow puncture (cytology, immunocytochemistry, histology, cytogenetics)

All examinations should be performed within 10 days after inclusion in the study. RT should begin at maximum 3 months after study inclusion.

8.1.2 Histologic diagnosis

8.1.2.1 Gastroscopy

Endoscopic procedures are of keen importance for the diagnosis of gastrointestinal lymphoma enabling an exact histologic classification. Therefore, a standardized and quality-controlled approach via „gastric mapping“ (Ruskoné-Fourmestreaux 2011) is mandatory in our study including the following procedures:

- 1 biopsy out of antrum and gastric body for urease rapid test
- 10 biopsies out of macroscopical suspicious areas (preservation in formalin and histologic examination)
- 1 biopsy out of any macroscopical unsuspecting quadrant of antrum and gastric body (8 in total)
- 2 biopsies out of gastric fundus
- documentation of endoscopy and the „gastric mapping“ on the documentation form

In case of a suspected gastric lymphoma after first endoscopy, the aforementioned biopsies likely require a second gastroscopy. For participating sites in Germany, it is recommended to send histologic samples to one of the 8 German reference centers of lymphoma pathology (see chapter 16.3 Appendices). Sites outside Germany consult their own routinely addressed pathologists.

8.1.2.2 Endoscopic bowel examination

In case of a suspected bowel involvement of lymphoma beyond the duodenum (e.g. seen as wall thickening on CT scans or during colonoscopy), endoscopic control should be performed by the least invasive way. Therefore, we recommend the use of a video capsule endoscopy to screen for mucosal changes. If a lymphoma involvement is to be proven, a colonoscopy and or double-balloon examination should be performed. In study centers, where a video capsule endoscopy is not available, ileocolonoscopy and double-balloon endoscopy should be employed first.

Importantly, in case of a **gastric lymphoma** prior to treatment the patients must undergo **colonoscopy** to confirm the absence of additional disease within the GI-tract.

If biopsies are taken, the following numbers are recommended:

- 4 biopsies from macroscopical suspicious areas (preservation in formalin and histologic examination)
- 2 biopsies each from terminal ileum/ colon ascendens/ colon transversum/ colon descendens/ sigma/ rectum

In case of a suspected intestinal lymphoma after first endoscopy, the aforementioned biopsies likely require a second gastroscopy. For participating sites in Germany, it is recommended to send histologic samples to one of the 8 German reference centers of lymphoma pathology (see chapter 16.3 Appendices). Sites outside Germany consult their own routinely addressed pathologists.

8.1.2.3 Endosonography

The following parameters have to be documented:

- Horizontal extension
- Longitudinal extension
- Depth infiltration (mucosa, submucosa, muscularis propria, serosa)
- Lymph node involvement

8.1.3 Staging

The modified Ann-Arbor-classification is used for staging:

stage	involvement
I	Involvement of a single gastrointestinal organ
I ₁	limited to mucosa or submucosa
I ₂	extension beyond submucosa
II	Involvement of a GI-organ and regional lymph nodes (LN) and/or extraorgan extension
II ₁	Involvement of a GI-organ and regional lymph nodes (II ₁) and/or adjacent organs (II ₁ E) infradiaphragmal
II ₂	Involvement of a GI-organ and lymph nodes beyond regional lymph nodes infradiaphragmal (II ₂) with a possible localized involvement of another extralymphatic organ (II ₂ E)
III	Involvement of a GI-organ and lymph node involvement infra- or supradiaphragmal with a possible localized involvement of another extralymphatic organ (III _E) or spleen (III _S) or both (III _S E)
IV	Diffuse or disseminated (non-GI) involvement with or without lymph-node involvement

Remarks:

- The suffix „E“ is only employed in case of an infiltrative extension („per continuitatem“) in adjacent organs (e.g. stomach → liver or esophagus or duodenum)
- In the case of simultaneous involvement of stomach and intestinum, no established staging exists
- Perigastric lymph node <1 cm are not considered to be involved in the GI NHL
- B-symptoms: As a weight loss > 10 % is potentially induced by the tumor location, only fever and night sweats are considered to be „B-symptoms“

8.2 Intermediate Visits

8.2.1 Intermediate visits 1-4 (IV-1=first day, IV-2=2nd day, IV-3=5th day, IV-4=last day of RT)

The intermediate visit 1 (IV -1) marks the beginning of RT, at the latest the assessment of quality of life with QLQ-C30 and STO-22 is to be performed before the start of RT .

The IV-2, IV-3 and IV-4 visits include blood draw!

At all intermediate visits (IV-1 – IV-4) acute radiogenic reactions must be documented (see Appendix 16.5 Adverse Reactions according to CTCAE).

Specific intermediate visits (IV-1, IV-2, IV-3, IV-4) will take place with IV-4 finishing the RT-treatment including the following aspects:

- Anamnesis
- Clinical examination: ECOG, weight, blood pressure
- **Quality of life assessment with QLQ-C30 and STO-22 (at IV-4)**
- **Blood draw after (!!) RT fraction (at IV-2/-3/-4):**
 - o –Routine: small blood count, LDH, GOT, GPT, alcalic phosphatase, γ -GT, bilirubin, creatinine.
 - o –**Research program (analyses at the University of Muenster!):**
Two 7.5 - 9 ml serum monovettes.
Centrifugation, freezing and storage see 3.1.3 and Appendix 16.7 (SOP BLOOD SAMPLES for RESEARCH PROGRAM)
Transmission of frozen blood samples to Radiobiology lab, Muenster at the cost of Dept. of Radiation Oncology, University Hospital Muenster).
- Acute radiogenic reactions must be documented (see Appendix 16.5. Adverse Reactions according to CTCAE)

Importantly, all treatments, therapies and taken medication till the end of the study should be documented on the respective clinical file. Any use of simultaneous anti-lymphoma treatment (e.g. chemo-, immunotherapy, steroids) is forbidden. Anyhow, corticosteroid intake for non-malignancies (e.g. asthma, inflammatory diseases) may be permitted up to a dose of 4 mg dexamethason or 20 mg of prednisone per day.

8.3 Follow-up examinations

8.3.1 FU-1

The first follow-up visit after RT takes place 6 weeks after the termination of RT \pm 5 days and should include the following examinations:

- Anamnesis
- Clinical examination: ECOG, weight, blood pressure
- Acute radiogenic reactions must be documented (see Appendix 16.5 Adverse Reactions according to CTCAE)

8.3.2 FU-2 – FU-6

The further exams take place quarterly in the first year after treatment (FU-2 – FU-5), afterwards an annual visit is scheduled (FU-6).

FU-2:	3 months after end of RT ± 3 weeks
FU-3:	6 months after end of RT ± 3 weeks
FU-4:	9 months after end of RT ± 3 weeks
FU-5:	12 months (1 year) after end of RT ± 3 weeks
FU-6:	24 months (2 years) after end of RT ± 3 weeks

The FU-2 and FU-3 visits include blood draw!

At all follow-up visits (FU-2 – FU-6) chronic radiogenic reactions must be documented (see Appendix 16.6 Adverse Reactions according to LENT SOMA).

Each follow-up visit consists of the following examinations:

- Anamnesis
- Clinical examination: ECOG, weight, blood pressure
(at FU-1/-2/-3/-5/-6)
- Quality of life assessment with QLQ-C30 and STO-22 (at FU-1/-2/-3)
- Endoscopy/ Endosonography (+ biopsies) (at FU-2/-3/-5/-6)
- CT-imaging (at FU-3/-5/-6)
- **Blood draw (at FU-2/-3):**
 - o –Routine: small blood count, LDH, GOT, GPT, alcalic phosphatase, γ-GT, bilirubin, creatinine.
 - o –**Research program (analyses at the University of Muenster!):**
Two 7.5 - 9 ml serum monovettes.
Centrifugation, freezing and storage see 3.1.3 and Appendix 16.7 (SOP BLOOD SAMPLES for RESEARCH PROGRAM)
Transmission of frozen blood samples to Radiobiology lab, Muenster at the cost of Dept. of Radiation Oncology, University Hospital Muenster
- Chronic radiogenic reactions must be documented (see Appendix 16.6 Adverse Reactions according to LENT SOMA)

The FU-6 is the study termination visit and ends the study regularly.

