9.1 Definitions

Adverse reactions (AR), acute toxicity: the **Common Terminology Criteria for Adverse Events (CTCAE)**, formerly called the Common Toxicity Criteria, are a set of criteria for the standardized classification of adverse reactions or effects of medical treatment used in cancer therapy. The CTCAE system is a product of the US National Cancer Institute (NCI).
ISRT 20 Gy in localized indolent GI-NHL, Study protocol, version 01, 23.08.2020 Page 27 of 75

The clinical relevant version 3.0 was released in 2006 (see Appendix 16.5). It uses a range of grades from 1 to 5, specific conditions and symptoms have values or descriptive comment for each level, the general guideline is:

Grade 1	mild
Grade 2	moderate
Grade 3	severe
Grade 4	life-threatening
Grade 5	death

Adverse reactions (AR), chronic toxicity: the **LENT SOMA** (Late Effects on Normal Tissue, Subjectiv, Objectiv, Management) score criteria are a set of criteria for the standardized classification of adverse effects of medical treatment used in cancer therapy. The LENT SOMA Tables for the gastrointestinal system with regard to the stomach and the small intestine are:

Grade 1/ 2/ 3/ 4. **S**ubjective, **O**bjective, **M**anagement, **A**lytic (see Appendix 16.6).

An **Adverse Event (AE)** is defined as an event impairing the patient's health status in comparison to the status before therapy regardless if this event is related to RT or not. Pre-existing medical conditions, planned hospitalizations, study diagnostic testing and procedures as well as an asymptomatic lymphocytosis are not considered as AE. Adverse events categorized as "serious" (SAE) are for e.g. results in death, illness requiring hospitalization, events deemed life-threatening, results in persistent or significant disability/incapacity, a congenital anomaly/birth defect or medically important condition. The grades of adverse events are defined as:

Grade 1	Mild; asymptomatic or mild symptoms; clinical or diagnostic observations only; intervention not indicated.
Grade 2	Moderate; minimal, local or noninvasive intervention indicated; limiting age-appropriate instrumental activity living
Grade 3	Severe or medically significant but not immediately life-threatening; hospitalization or prolongation of hospitalization indicated; disabling; limiting self care activity of daily living
Grade 4	Life-threatening consequences; urgent intervention indicated.
Grade 5	Death related to AE

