Subjective Epigastric distress Emesis Pain	Occasional & minimal Occasional Occasional & minimal	Intermittent & tolerable Intermittent Intermittent & tolerable	Persistent & intense Persistent Persistent & intense	Refractory & excruciating Refractory Refractory & excruciating	Instructions Score the 13 SOM parameters with 1-4
Objective Hematemesis Weight loss from time of treatment Melena	Occasional \geq 5%- 10% Occult / Occasional, normal hemoglobin Superficial, \leq 1cm ² > 2/3 normal diameter	Intermittent > 10%-20% Intermittent, < 10% decrease in hemoglobin	Persistent >20% -30% Persistent, 10% - 20% decrease in hemoglobin	Refractory >30% Refractory or frank blood, > 20% decrease in hemoglobin	(Score = 0 if there are no toxicities) Total the score and divide by 13

Ulceration Stricture (Antro-pyloric region)		Superficial, > 1 cm ² 1/3 - 2/3 normal diameter	Deep ulcer < 1/3 normal diameter	Perforation, fistulae Complete obstruction	
M anagement Epigastric distress / Emesis Pain Bleeding Ulceration Stricture	Diet modification, antacids Occasional non-narcotic Iron therapy	Intermittent prescription medication Regular non-narcotic Occasional transfusion	Persistent medical management Regular narcotic Frequent transfusions Medical intervention Medical intervention	Surgical intervention Surgical intervention Embolization, coagulation or surgical intervention Surgical intervention Surgical intervention	LENT Score:
A nalytic Barium radiography Endoscopy CT MRI	Assessment of lumen and peristalsis Assessment of lumen and mucosal surface Assessment of wall thickness, sinus and fistula formation Assessment of wall thickness, sinus and fistula formation				Y/N Date: Y/N Date: Y/N Date: Y/N Date:

SMALL INTESTINE / COLON

	GRADE 1	GRADE 2	GRADE 3	GRADE 4	SCORING
S ubjective Stool frequency Stool consistency Pain	2-4per day Bulky Occasional & minimal	5-8per day Loose Intermittent & tolerable	> 8 per day Mucous, dark, watery Persistent & intense	Refractory diarrhea Refractory / Rebound	Instructions Score the 13 SOM parameters with 1-4

Constipation	3 - 4 per week	On!, 2 per week	Only 1 per week	No stool in 10 days	
O bjective Melena	Occult / Occasional	Intermittent & tolerable, normal hemoglobin	Persistent, 10% - 20% decrease in hemoglobin	Refractory or frank blood, >20% decrease in hemoglobin	(Score = 0 if there are no toxicities) Total the score and divide by 13
Weight loss from time of treatment	≥ 5%-10%	> 10% -20%	>20% -30%	>30%	

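### LENT SOMA has no score before radiotherapy, and the first CTCAE score is not fixed as preceding the first fraction, so worsening from the pre-treatment state cannot be shown reliably

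*Protocol*

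**What the plan says.** **When each instrument is used.** The visit table in Protocol section 8 starts the acute reaction row at IV-1 and the chronic reaction row at FU-2. The text agrees. For CTCAE, section 8.2.1 says: "At all intermediate visits (IV-1 – IV-4) acute radiogenic reactions must be documented". For LENT SOMA, section 8.3.2 says that at FU-2 to FU-6 "chronic radiogenic reactions must be documented (see Appendix 16.6 Adverse Reactions according to LENT SOMA". FU-2 falls 3 months after the end of radiotherapy. The baseline visit (section 8.1) has a form for neither instrument.

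**What is recorded before radiotherapy.** Section 8.1 lists symptoms with date of onset, medication, examination with weight, blood analysis, QLQ-C30 and STO22, CT, upper endoscopy with biopsy, endosonography, capsule endoscopy and colonoscopy.

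**Timing at the radiotherapy visits.** For quality of life, section 8.2.1 says "at the latest the assessment of quality of life with QLQ-C30 and STO-22 is to be performed before the start of RT". For blood it says "Blood draw after (!!) RT fraction (at IV-2/-3/-4". It gives no such order for toxicity scoring at IV-1.

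**Definitions.** Section 9.1 defines an adverse event by impairment of the patient's "health status in comparison to the status before therapy" and excludes pre-existing conditions. The paragraphs on adverse reactions, which name the instruments for the acute and chronic toxicity endpoints, contain neither element.

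**Scoring rule.** The stomach table in Appendix F instructs: "Score = 0 if there are no toxicities) Total the score and divide by 13".

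**Use of the grades.** Acute and chronic toxicities are secondary endpoints (section 3.2.2). Under section 9.2, an accumulation of grade 3 or 4 reactions on either instrument, compared with earlier prospective trials, may lead to early termination.

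**The concern.** Epigastric distress, pain, vomiting, bleeding and ulceration are possible late effects of gastric irradiation. They can also be features of the gastric or duodenal lymphoma being treated. Separating the two requires a grade from before treatment on the same scale, and the schedule does not secure one.

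Safety is part of the primary objective (section 3.1.1), and lower risk of adverse reactions is one of the stated justifications for the single-arm design (section 4). With no control arm, each patient's own state before radiotherapy is the only reference inside the trial. If disease findings enter the toxicity grades, toxicity at 20 Gy is overstated. The overstatement would shrink as the lymphoma responds, so late toxicity could appear to follow response. The same grades feed the section 9.2 comparison.

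**Working it through.** The Protocol gives no figure on this point, so the check is a comparison of sections plus two illustrations.

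**1. Is there a grade before radiotherapy?**
- LENT SOMA: no. It is first scored at FU-2, in both table and text.
- CTCAE: not assured. IV-1 is on the first day of radiotherapy, and the order relative to the fraction is not stated. Quality of life and the research blood samples do have assured measurements before treatment.

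**2. Can the items be graded without one?** The stomach table in Appendix F has 3 subjective + 5 objective + 5 management = 13 items.
- Weight loss is the only item written as a change from the time of treatment. Melena is partly anchored, through the fall in haemoglobin.
- Epigastric distress, emesis, pain, hematemesis, ulceration and stricture are graded as found.
- In Appendix E some CTCAE items are anchored to baseline (fatigue, diarrhea, weight). Others, such as heartburn, gastritis and pain, are not.
- Weight and laboratory items could be regraded later from recorded baseline values. Symptom and management items could not be, and ulceration only as far as the endoscopy report happens to allow.

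**3. Effect on one patient's score.** Score = sum of grades / 13. Suppose epigastric distress, pain and an ulcer, all due to lymphoma, persist unchanged at grade 2 and are graded as found. The score is (2 + 2 + 2)/13 = 6/13 = 0.46 with no radiation effect.

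**4. Effect on a rate, on assumed inputs only.** Let t be the true proportion with radiation toxicity and q the proportion with a persisting, gradable finding from before treatment, taken as independent, with nothing attributed to the lymphoma. Apparent rate = 1 − (1 − q)(1 − t). With t = 10%:

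| q | Apparent rate | Extra patients of 83 = 83 × q × 0.90 |
|---|---|---|
| 10% | 1 − 0.90 × 0.90 = 19% | 7.5 |
| 20% | 1 − 0.80 × 0.90 = 28% | 14.9 |
| 30% | 1 − 0.70 × 0.90 = 37% | 22.4 |

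Neither q nor t is in the Protocol; 83 is the planned number assigned. The causality rating would lower these counts by an unknown amount, so they show the mechanism and are not an estimate.

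**5. Do later steps repair the gap?** Section 9.2.1 has the lead investigators and study center rate the relation of each adverse reaction to treatment. No rule says whether reactions rated unlikely or not related leave the toxicity endpoints or the section 9.2 counts. The clause in section 9.2 on tumor events covers progression, not disease that persists. Persisting disease is foreseen: responding residual disease counts as partial remission, and no change is a response category (section 3.2.1).

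**The case against.** A reader might infer that no score exists before radiotherapy on either instrument, and that symptoms of the lymphoma are therefore counted as radiation toxicity. The document does not support that.

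- **IV-1 can be a baseline.** CTCAE scored that day before the fraction would serve. The fault is the unstated order. Even if scored afterwards, only one 2 Gy fraction has been given.
- **Sites are told to record radiogenic reactions.** Section 8.2.1 says "acute radiogenic reactions must be documented (see Appendix 16.5 Adverse Reactions according to CTCAE", section 8.3.2 uses matching words for chronic reactions, and the LENT SOMA rule sets the score to zero where there is no toxicity. An unchanged symptom or ulcer from before treatment should not be scored at all. It can be misattributed, but the plan does not direct that it be counted.
- **There is an attribution step.** Section 9.2.1 covers adverse reactions as well as events and allows other diseases or lymphoma progression as the better explanation.
- **The baseline work-up is full.** Symptoms with onset, quality of life and endoscopy with biopsy let an assessor see that a finding came before treatment. Endoscopy is repeated at FU-2, FU-3, FU-5 and FU-6.
- **Part of the remedy is analysis detail.** A rule for worsening from baseline may stand in a statistical analysis plan that is not shown.

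All of this stands, and it limits the point. It does not remove it. Ungraded records can show that a finding existed, but not reliably whether it rose by a grade. An analysis plan can define worsening only if a grade was collected. It is also not shown that the section 9.2 comparison is biased in one direction, because the Protocol does not say how the earlier trials scored toxicity.

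**Conclusion.** The point holds as a gap in measurement. LENT SOMA has no score before radiotherapy, the IV-1 CTCAE score is not fixed as preceding the first fraction, and the adverse reaction definitions make no comparison with the earlier state. Misattribution of persisting disease findings is possible. For symptom items on LENT SOMA, worsening by grade cannot be determined.

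The size is unknown. The 6/13 score is exact arithmetic on a hypothetical patient. The apparent rates of 19% to 37% rest wholly on assumed inputs and ignore causality attribution. It is also unclear which CTCAE items are captured, since Appendix E marks them by highlighting that the available text does not show. Toxicity is a secondary endpoint, so the test of response rate is unaffected. The change is still worth making, because the missing grade cannot be recovered once treatment has begun and costs little to collect.

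**What to change.** 1. In the section 8 visit table and in section 8.1 or 8.2.1, schedule CTCAE and LENT SOMA scoring at the baseline visit, or at IV-1 expressly before the first fraction.
2. In section 9.1, give the adverse reaction definitions the comparison with the state before therapy that the adverse event definition already has.
3. Report acute and chronic toxicity, including the grade 3 and 4 counts used in section 9.2, as worsening from the pre-radiotherapy grade, with raw grades alongside.
4. State how the section 9.2.1 causality rating enters the toxicity endpoints and those counts.

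The cost is one extra form per patient, at a visit where history, examination, laboratory tests and endoscopy are already done or at hand. No new procedure is needed. For patients already treated, any grade reconstructed from the records should be labelled as retrospective.
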